3.2 Sample Size

We estimate an enrollment rate of 1-2 participants per month, for an enrollment period lasting 6 months. It is expected that approximately 50% of patients being referred to the study will meet eligibility criteria at the time of screening. The study team thus aims to screen 24 or more potential participants.

3.3 Eligibility Criteria

3.3.1 Inclusion Criteria

In order to be eligible to participate in this study, an individual must meet all of the following criteria:

- 1. Must have a diagnosis of a stage 3 or 4 primary GI (i.e., pancreatic, colorectal, hepatocellular, biliary, and gastro-esophageal) cancer.
- 2. Must be willing to sign the informed consent form (ICF) and follow the study procedures as outlined in the ICF for the duration of the study.
- 3. Must be 18 years or older.
- 4. Must speak English and/or Spanish.
- 5. Must have a Palliative Performance Score (PPS v. 2.0) greater than or equal to 40%. *Note: See Appendix 1.*
- 6. Must be able to swallow liquid oral medication.

Pilot Study - Ketamine Page 18 of 55

- 7. Must self-report moderate-to-severe demoralization (DS-II≥10 per Demoralization Scale-II) that is stable.
 - Note: Stable is defined as DS-II ≥10/32 two times ≥7 days apart.
- 8. Must discontinue the following medications and refrain from taking them for the duration of study participation (participants who require these medications will be taken off study):
 - a) Lamotrigine
 - b) Clozapine
 - c) PRN (as-needed) anxiolytics
 Note: Benzodiazepine use may be allowed if used in a regular, scheduled way. Consultation
 with the Principal Investigator is recommended.
 - d) Dopamine agonists
 - e) Lithium
- 9. Female-born participants of child-bearing potential with male-born partners must use highly effective contraception for at least 1 month prior to ketamine administration (on day 0) and agree to use such a method for an additional 2 months after ketamine administration.
- 10. Male-born participants with female-born partners of child-bearing potential must use highly effective contraception for at least 1 month prior to ketamine administration and agree to use such a method for an additional 2 months after ketamine administration.

Note: Highly effective contraception include:

- Intrauterine device (IUD)
- Intrauterine hormone-releasing system (IUS)
- Non-oral hormonal methods, including injected, intravaginal, implanted, transdermal
- Oral hormones plus a barrier contraception (condom, diaphragm, or spermicide)
- Double barrier method (at least two of the following: condom, diaphragm, and spermicide)
- Vasectomy
- Abstinence from penile-vaginal intercourse*
 *The reliability of abstinence should be evaluated carefully with the participant in relation to their general lifestyle. An additional acceptable birth control method should be discussed with the participant in case they decide to engage in penile-vaginal intercourse during the course of the study.
- 11. Must agree to the following lifestyle considerations:
 - a) Continue receiving psychotherapy or other behavioral interventions for mental health as usual. Current interventions should not be stopped, and new interventions should not be started during the study period once participants are enrolled in the study.
 - b) Consume no more than a modest quantity (e.g., 1 cup) of caffeine or xanthine-containing products (e.g., coffee or tea) the morning of receiving ketamine (on Day 0/Visit 4).
 - c) Abstain from alcohol for 24 hours before receiving ketamine.
 - d) Abstain from using any nicotine-containing products (including nicotine patches) for 3 hours before receiving ketamine.
 - e) If cannabis products are used regularly, participants will be asked to continue using their regular amount but will be asked not to use cannabis within 24 hours prior to receiving ketamine.
 - f) If prescribed a regular dose of benzodiazepines, will be asked not to take their medication the morning of the ketamine administration visit.
 - g) If taking any psychostimulants (e.g., methylphenidate), will be asked not to take psychostimulant drugs (other than caffeine) the morning of the ketamine administration visit.
 - h) Will be advised to maintain their usual opioid regimen.

Pilot Study - Ketamine Page 19 of 55

Note: Input will be obtained from the participant's regular clinical providers on appropriate pain management for the participant during the study, particularly in the case of analgesics associated with adverse reactions of concern with ketamine (e.g., tramadol and any opioid may increase the risk of respiratory depression from ketamine).

3.3.2 Exclusion Criteria

An individual who meets any of the following criteria will be excluded from participation in this study:

- 1. Has a known allergic or severe reactions to the non-psychoactive components of liquid ketamine.
- 2. Has received treatment with another investigational drug or intervention within 1 month of signing Informed Consent Form (ICF).
- 3. If deemed by the clinical judgment of the study investigators to be unsafe for undergoing the intervention.
- 4. Has used ketamine within 5 years of signing ICF.

 Note: Ketamine used for anesthesia for medical procedures is permissible.
- 5. Has a lifetime use of ketamine for non-anesthetic purposes ≥10 times.
- 6. Has a history of intracerebral hemorrhage.
- 7. Has cognitive impairment sufficient to impede the ability to complete study tasks.
- 8. Has had delirium/encephalopathy within 3 months of signing ICF.
- 9. Has a history of intracranial hemorrhage.
- 10. Has had a stroke (embolic) within 12 months of signing ICF.
- 11. Has had a seizure within 6 months of signing ICF.
- 12. Currently has an intracranial mass (e.g., primary tumor or brain metastasis).
- 13. Has an advanced stage of a neurologic disease that puts patients at elevated risk for psychosis (e.g., Parkinson or Huntington disease).
- 14. Has a history of a primary psychotic disorder or primary bipolar disorder I or II (determined by QuickSCID-5).
- 15. Has a history of dissociative disorder.
- 16. Has active suicidal ideation with intent in the last 2 months (Suicidal ideation score ≥4 and Reason for ideation >1 on C-SSRS).
 - Note: This does not include requesting medical aid in dying.
- 17. Is currently receiving electroconvulsive therapy (ECT), transcranial magnetic stimulation (TMS) or similar somatic therapies.
- 18. Has baseline hypertension (≥150 SBP or ≥90 DBP), after repeated measurements.

 Note: Participants with hypertension that has been controlled by medication down to <150 SBP and <90 DBP will be allowed to participate.
- 19. Has a history of aneurysmal vascular disease or dissection (including thoracic and abdominal aorta, intracranial, and peripheral arterial vessels) or arteriovenous malformation.
- 20. Has had cardiac arrest within 12 months of signing ICF.
- 21. Has had a myocardial infarction within 12 months of signing ICF.
- 22. Has QTcf >480msec on 12-lead EKG.
 - Note: Participants may qualify for the study if QTc 480-500 msec on one EKG, but then ≤480 msec on repeat EKG taken >1 day later. If QT-prolonging medications are started or increased in dose after enrollment and prior to ketamine administration, a repeat EKG must be done >12-hours after this change in order to assure continued safe enrollment in the trial.
- 23. Has clinically significant arrhythmia defined as:
 - a) Ventricular fibrillation or ventricular tachycardia within 1 year of signing ICF
 - b) Bradycardia, severe, within 1 year of signing ICF Note: Participants with pacemakers will be considered to be eligible at the discretion of the Principal Investigator.

Pilot Study - Ketamine Page 20 of 55

- c) Atrial fibrillation, without rate or rhythm control
- d) Supraventricular tachycardia (SVT), without standard treatment
- e) Other clinically significant arrhythmias (e.g., Wolf Parkinson White)
- 24. Has symptomatic congestive heart failure (NYHA Class II-IV)
- 25. Has severe obstructive intracardiac abnormalities (e.g., aortic stenosis)
- 26. Has any current condition where physical activity is associated with palpitations, anginal pain or syncope.
- 27. Is unable to protect their own airway due to dysphagia, difficulty swallowing, or a neurologic disease resulting in a risk of aspiration.
- 28. Has a history of flash pulmonary edema within 12 months of signing ICF.
- 29. Has a diagnosis of moderate or severe pulmonary hypertension.
- 30. Needs supplemental oxygen (intermittent or continuous).
- 31. Has current intractable nausea/vomiting/diarrhea.
- 32. Meets the following laboratory parameters:
 - a) Asymptomatic ALT or AST ≥5x ULN.
 - b) Symptomatic ALT or AST ≥2x ULN.
 - c) Total bilirubin > 2x ULN [Gilbert syndrome is allowed]
 - d) Alkaline phosphatase >5x ULN
 - e) INR > 2.5 for patients with any history of cirrhosis or gastrointestinal bleeding within 6 months of signing ICF. (An INR measurement is otherwise not required).
 - f) Renal insufficiency (i.e., eGFR < 30mL/min/1.73 m2 [using the 2021 Chronic Kidney Disease Epidemiology Collaboration (CKD-EPI) Creatinine Equation], CrCl < 30mL/min [using the Cockcroft-Gault Equation], or current dialysis)
- 33. Is currently pregnant or breastfeeding.
- 34. Has insulin-dependent diabetes with diabetes-related hospitalization within 6 months of signing ICF.

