3.6 Duration of Treatment

Ketamine treatment will be given on Day 0. K-MaP therapy will continue from Day -13 to Day 14 (about 28 days) or until:

- Inter-current illness that prevents further administration of treatment;
- Unacceptable adverse event(s);
- Participant decides to withdraw from the study;
- Significant participant non-compliance with protocol;
- If the participant meets an exclusion criterion (either newly developed or not previously recognized) that precludes further study participation
- General or specific changes in the participant's condition render the participant unacceptable for further treatment in the judgment of the investigator.

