6.1 Study Calendar

	≥7, ≤28 days before Enrollment	Day -28 to -7	Day -13 to -4	Day -12 to -1	Day 0	Day 3 +/- 2 days	Day 7 +/- 2 days	Day 11 +/- 2 days	Day 14 +/-2 days	Day 35 +/- 2 days
	Phone Screening	V1 [Enrollment/ Baseline]	V2 [MaP Session 1]	V3 [MaP Session 2]	V4 [Randomization/ Ketamine]	V5 [MaP Session 3]	V6	V7 [MaP Session 4]	8/	6/
Verbal Waiver of Consent; Phone Screen	х									
Informed Consent Form		х								
Brief Clinical Interview ¹		х			х					
Interview on Acceptability and Tolerability										х
Demographics		х								
C-SSRS		х	х	х	х	Х	х	х	х	х
Physical exam		х								
Vitals (BP, HR) ²		х			х					

Pilot Study - Ketamine Page 32 of 55

¹ Partcipants will be briefly interviewed by the study team at baseline. The baseline interview will asses for clinical fit for K-MaP by evaluating participant expectations and prior experiences of altered states of consciousness. On Day 0/Visit 4, around 1.5-2 hours after ketamine administration (when the drug effects wear off), the facilitators will engage the participant in a therapeutic interview to explore the experience they had. The Day 0/Visit 4 interview will be video and audio recorded.

² Vitals will be taken at baseline, and prior to ketamine administration on Day 0/Visit 4. On Day 0, vital signs (heart rate and blood pressure) will be recorded at 10 minutes prior to drug ingestion ("Minute -10"), and then 30, 60, 90, 120, and 180 minutes after drug ingestion. If at 180 minutes blood pressure is meaningfully elevated compared to Minute -10, blood pressure will continue to be repeatedly assessed until it has returned to near its Minute -10 measurement. Respiratory rate and oxygen saturation will be assessed as needed.

	≥7, ≤28 days before Enrollment	Day -28 to -7	Day -13 to -4	Day -12 to -1	Day 0	Day 3 +/- 2 days	Day 7 +/- 2 days	Day 11 +/- 2 days	Day 14 +/-2 days	Day 35 +/- 2 days
	Phone Screening	V1 [Enrollment/ Baseline]	V2 [MaP Session 1]	V3 [MaP Session 2]	V4 [Randomization/ Ketamine]	V5 [MaP Session 3]	9/	V7 [MaP Session 4]	V8	6/
Height and Weight		х								
Medical/Psychiatric Hx		х								
PPSv2		Х								
Eligibility Verification		X								
Randomization					х					
LFTs, Creatinine, Electrolytes, PT/INR ³		х								
12-lead EKG ⁴		х								
DS-II ⁵	Х	Х			х		Х		Х	х

- Electrolytes: Sodium, potassium, carbon dioxide, and chloride.
- Liver function tests: Total bilirubin, ALT, AST, and alkaline phosphatase.

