- Cogulation tests: PT/INR (for patients with a history of cirrhosis or GI bleed within past 6 months)
- Renal function: Creatinine.

Pilot Study - Ketamine Page 33 of 55

³ The following laboratory tests are required at baseline:

⁴ EKG is required at baseline.

⁵ DS-II will be measured two times before enrollment. Once over the phone after verbal waiver of consent, and tagain, ≥7 days apart, after the participant has signed the informed consent form and started screening procedures. DS-II will also be measured at Visits 4 (before Ketamine administration), 6, 8, and 9.

	≥7, ≤28 days before Enrollment	Day -28 to -7	Day -13 to -4	Day -12 to -1	Day 0	Day 3 +/- 2 days	Day 7 +/- 2 days	Day 11 +/- 2 days	Day 14 +/-2 days	Day 35 +/- 2 days
	Phone Screening	V1 [Enrollment/ Baseline]	V2 [MaP Session 1]	V3 [MaP Session 2]	V4 [Randomization/ Ketamine]	V5 [MaP Session 3]	V6	V7 [MaP Session 4]	88	۸9
PHQ9, GAD7, BPI-SF, <24hr MME,		Х			х		х		x	х
MAIA-2					х		х			
FACIT-Pai14		Х			х		х		х	х
CGI-S, DI, GRID-HAMD6		х							х	х
MEQ, CEQ					х					
MaP Therapy Session ⁶			х	х		х		х		
Ketamine therapy (day of administration) ⁷					x					
HBD Task ⁸					х					

Pilot Study - Ketamine Page 34 of 55

⁶ It will be recommended that att least one MaP session prior to Day 0/Visit 4 occur in-person (i.e., MaP sessions on Visit 2 or 3).

⁷ The ketamine administration visit will last approximately 4-5 hours. Patients will leave the premises once they are deemed to be free of the acute effects of ketamine, at least 3 hours have passed since ingestion of the oral drug-cranberry juice solution, and the study team confirms they are in the presence of a caregiver. In the event that a participant did not arrange a caregiver to accompany them home, the participant will be required to stay with the study staff and will be escorted outside by a study team member who will accompany them home in a taxi, Lyft, or Uber.

⁸ The Heartbeat Detection (HBD) task will be administered by a trained provider twice on the day of ketamine dosing. The tasks takes about 8 minutes to complete and will administered once a least 15 minutes prior to receipt of the oral drug-cranberry juice solution and again at least 3 hours after receipt of this oral solution.

	≥7, ≤28 days before Enrollment	Day -28 to -7	Day -13 to -4	Day -12 to -1	Day 0	Day 3 +/- 2 days	Day 7 +/- 2 days	Day 11 +/- 2 days	Day 14 +/-2 days	Day 35 +/- 2 days

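### Pregnancy is an exclusion, but no pregnancy test is scheduled and eligibility is verified only at Visit 1, 7 to 28 days before dosing

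*Combined protocol and SAP*

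**What the plan says.** **Criteria.** Exclusion 33 (Section 3.3.2) is "Is currently pregnant or breastfeeding", with no method of ascertainment. Exclusion 14 is "Has a history of a primary psychotic disorder or primary bipolar disorder I or II (determined by QuickSCID-5", so its instrument is named. Inclusion 9 (Section 3.3.1) admits female-born participants of child-bearing potential; those with male-born partners "must use highly effective contraception for at least 1 month prior to ketamine administration (on day 0" and for two months afterwards.

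**Baseline tests.** The laboratory row of the Section 6.1 calendar is "LFTs, Creatinine, Electrolytes, PT/INR", marked at Visit 1. Footnote 3 opens with "The following laboratory tests are required at baseline" and then lists electrolytes ("Sodium, potassium, carbon dioxide, and chloride"), liver tests ("Total bilirubin, ALT, AST, and alkaline phosphatase"), PT/INR for patients with cirrhosis or a recent GI bleed, and creatinine.

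**Verification and dosing.** The Eligibility Verification row is marked once, at Visit 1 (Day -28 to -7). Randomization and ketamine are on Day 0 (Visit 4). Section 3.1 allows randomization only if all criteria are met. Among the reasons for ending treatment, Section 3.6 gives: "If the participant meets an exclusion criterion (either newly developed or not previously recognized) that precludes further study participation".

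**The concern.** An exclusion protects participants only if some procedure can detect the excluded state before exposure. For pregnancy, the documents state the exclusion and require contraception around dosing, so they treat exposure as a risk to be controlled, yet they schedule nothing that would reveal a pregnancy. Ketamine is given once. If a pregnancy is recognized only after Day 0, the stopping rule in Section 3.6 can no longer prevent the exposure.

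The calendar matters because Section 6 says that the study procedures are detailed in that section and outlined in the calendar, and Section 9.8 ties data entry to the study calendar. An assessment found in neither place has no defined time and may have no form on which to record it.

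**Working it through.** There is no figure in the plan to reproduce. The check sets the eligibility criteria against the scheduled assessments; the only arithmetic is one interval.

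**1. Criteria that rest on a measurement or instrument, and where each is scheduled**

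| Criterion | Measure | Scheduled in Section 6.1 |
|---|---|---|
| Inclusion 5 | PPSv2 | Visit 1 |
| Inclusion 7 | DS-II | Phone screen and Visit 1 |
| Exclusion 16 | C-SSRS | Visit 1 and every later visit |
| Exclusion 18 | Blood pressure | Visits 1 and 4 |
| Exclusion 22 | 12-lead EKG | Visit 1; repeat if QT-prolonging drugs are started or increased (Section 3.3.2) |
| Exclusion 32 | Liver and renal tests, INR for some | Visit 1 |
| Exclusion 14 | QuickSCID-5 | No row; medical/psychiatric history at Visit 1 |
| Exclusion 33 (pregnancy) | None named | No row |

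The calendar is split over several pages, but footnote 3 and the Section 6 instrument list are prose and agree with it. Neither contains a pregnancy test or QuickSCID-5.

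**2. Interval from verification to dosing**

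Interval = Day 0 minus the day of Visit 1.
- Earliest Visit 1: 0 - (-28) = 28 days.
- Latest Visit 1: 0 - (-7) = 7 days.

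Dosing therefore follows the only scheduled verification by 7 to 28 days.

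**3. What happens on Day 0 before dosing**

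Sections 5 and 6 place the patient-reported scales, the first heartbeat detection task, and heart rate and blood pressure before ingestion. The calendar also marks concomitant medications, adverse events and C-SSRS at Visit 4. None of these detects pregnancy. The Visit 4 interview cannot serve as a pre-dose check: calendar footnote 1 puts it about 1.5 to 2 hours after ketamine.

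**4. Two routes to dosing a pregnant participant without a calendar deviation**

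- The pregnancy exists at Visit 1 but is unrecognized. No test is done, eligibility is verified on self-report, and nothing later would find it.
- The pregnancy begins after Visit 1. Eligibility was correctly verified then and is not scheduled for verification again.

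**5. QuickSCID-5**

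It is named in exclusion 14 and nowhere else. The baseline interview described in footnote 1 covers expectations and earlier altered states, not psychiatric diagnosis. The instrument is therefore required but has no scheduled visit.

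**The case against.** The best reply is that the protocol already controls this risk. Randomization depends on meeting all criteria, Section 3.6 covers exclusions that develop or are recognized later, exclusion 3 leaves room for investigator judgment, and concomitant medications, adverse events and C-SSRS are reviewed at Visits 2, 3 and 4. Contraception is required beforehand, and Section 3.5.2 says that GI cancers occur mostly at age 60 or older. All of this stands and lowers the likelihood. None of it is a means of detecting pregnancy, so the gap remains.

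Three stronger readings are tempting, and the documents do not support them.

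- A reader might infer that exclusion 14 goes unassessed, or might count it with exclusion 33 as a criterion without any assessment. Exclusion 14 itself mandates QuickSCID-5, and psychiatric history is taken at Visit 1. Section 6 mainly describes outcome and safety measures, so a screening-only instrument need not appear there. A lifetime history also does not go out of date in 28 days. Nor is the lack of a named test unusual: breastfeeding, dissociative disorder and other exclusions can rest on history.
- A reader might infer that one month of contraception cannot fit into a consent-to-dose window of at most 28 days. The requirement counts back from ketamine, not from consent, and may be met by contraception already in use. First contact is also earlier: phone screening is 7 to 28 days before enrollment, so contact to dosing spans 7 + 7 = 14 to 28 + 28 = 56 days. There is no contradiction.
- A reader might turn one wrongly included participant into a share of a six-patient arm and call it bias. No formal efficacy tests are planned (Section 9.1.1), and nothing in the documents ties such a share to a per-arm consequence.

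**Conclusion.** The point holds for pregnancy. Scheduled pregnancy tests number zero, eligibility is verified once, and that verification is 7 to 28 days old when the single dose is given. Full adherence to the calendar does not rule out dosing a participant with an unrecognized or new pregnancy.

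The number exposed to this gap is probably small, but the documents do not say how many of the 12 may be of child-bearing potential, so no probability can be given. The conclusion assumes that no separate site procedure supplies the test; the protocol refers to none.

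For QuickSCID-5 the finding is only a scheduling gap. Neither part alters a sample-size or error-rate figure. This is an eligibility and safety matter that should be corrected, not a flaw in the analysis.

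**What to change.** Reconcile the Section 6.1 calendar and footnote 3 with the Section 3.3 criteria:

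- (a) Add a pregnancy test for participants of child-bearing potential at Visit 1 and at Visit 4 before randomization.
- (b) Add a QuickSCID-5 row at Visit 1.
- (c) Mark Eligibility Verification also at Visit 4, before randomization. It can use the concomitant-medication, adverse-event, C-SSRS and vital-sign checks already scheduled, provided they are done before dosing. Of these, only the vital signs have a stated pre-dose time at Visit 4, and Section 5 describes the C-SSRS there after the drug effects begin to wear off. The calendar should therefore state which of these checks come before randomization, or rely on the Visit 3 C-SSRS. The Visit 4 interview should not be used, since it follows dosing.

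The cost is a calendar edit, a low-cost test for a few participants, and a few minutes of visit time. QuickSCID-5 adds no new burden because exclusion 14 already requires it. Doses, arms, sample size and analyses are unchanged.

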3.4 Inclusion and Recruitment of Women and Minorities

3.4.1 Eligibility of Women and Minorities

Individuals of any sex/gender, race, or ethnicity are eligible for this study.

The study recruitment strategy aims to achieve representation of minority groups that reflects the demographics of the affected population in the catchment area. This includes consideration of outreach programs to conduct or support recruitment of women and members of minority groups as participants and design of the clinical trial to include a valid analysis plan of whether variables being studied in the trial affect women or minority groups.

3.5 Inclusion Across the Lifespan

3.5.1 Age Range of Participants

Individuals ages 18 and over are eligible for this study. Children are excluded from the study because insufficient data on prospective benefits and/or adverse events for a treatment that includes potentially fatal risks poses unacceptable risk to children.

